1.4 Pharmacokinetic Analysis

Pharmacokinetic parameters will be analyzed by Mithra Biotechnology Inc. All pharmacokinetic parameters data will be provided to sponsor directly, no data handling, data listing nor statistical analysis on such data will be done by A2 Healthcare.

- 2.2 Endpoints
 - 2.2.2 Secondary endpoints
 - 2 Pharmacokinetic parameters of marker ingredient in Careseng 1370, 20(S)-protopanaxadiol (PPD) and its metabolites

Careseng 1370 for Healthy Volunteers

3 Protocol Versions and Protocol Amendments

The first subject was enrolled on 14AUG2020, and the last subject is expected to be dismissed on MAR2022. Amendments relevant to important statistical-related changes are summarized in table below, and Table/Figure/Listing programming will be based on the latest version of protocol.

Summary of important statistical-related changes for protocol version V4.0
Additional time points for PK blood sampling for Dose level B and C

Summary of important statistical-related changes for protocol version V5.0

Addition of 1 lower dose cohort (level D), and the corresponding information

Version 1.0, 08-SEP-2022 Protocol No.: Careseng 1370-01

Careseng 1370 for Healthy Volunteers

4 Mock-up Tables and Figures

The Mock-up "TABLES and FIGURES" is planned according to ICH E3, in which relevant CSR section is 14. The words shadowed below are to be adjusted or repeated upon real data, or just for notification.

Columns {Label, Dose Level} will be included in the table with the analyzed population specified. In the mock table below, only the Label with one dose level column were presented to show the descriptive/inferential statistics to be displayed in the final tabulation.

Version 1.0, 08-SEP-2022 Protocol No.: Careseng 1370-01 Confidential Page 5 of 20

Careseng 1370 for Healthy Volunteers

Instructions and Abbreviations:

(1) Site ID [C]:

Site ID	Full Name	
1	Taipei Medical University Hospital (TMUH)	

(2) Dose Level:

- A (1 sachet/day): Careseng 1370 1 sachet before breakfast for consecutive 5 days
- B (2 sachets/day): Careseng 1370 1 sachet before breakfast and 1 sachet before lunch for consecutive 5 days
- C (3 sachets/day): Careseng 1370 1 sachet before breakfast and 2 sachets before lunch for consecutive 5 days
- D (1 sachet/day): Careseng 1370 1 sachet before breakfast on 1st, 3rd and 5th days (modified cohort)

(3) Population

- Intention-to-Treat (ITT) Population:
 - Volunteers receive any Careseng 1370
- Maximum Tolerated Dose (MTD)-Evaluable Population:
 - 1. A subset of ITT population
 - 2. Experiences DLT OR with at least 80% of study drug compliance and has exposed to Careseng 1370 for at least 4 days

(4) For Visit Name (in Tables and Figures) and Visit Code (in Subject Data Listing):

Visit No.	Visit Description	Visit Day	Visit Name	Visit Code
1	Visit 1 Screening Visit	-14 ∼ -1	Visit 1 (Screening)	V01
2	Visit 2 Hospitalization: Day -1 to Day 1	1	Visit 2 (Day 1)	V02D01
3	Visit 3 Discharge: Day 2	2	Visit 3 (Day 2)	V03D02
4	Visit 4: Day 3	3	Visit 4 (Day 3)	V04D03
5	Visit 5: Day 4	4	Visit 5 (Day 4)	V05D04
6	Visit 6 Hospitalization: Day 4 to Day 5	5	Visit 6 (Day 5)	V06D05
7	Visit 7 Discharge: Day 6 (24±2 hrs post-last dose)	6	Visit 7 (Day 6)	V07D06
8	Visit 8 Follow-up Visit: Day 7 (48±2 hrs post-last dose)	7	Visit 8 (Day 7)	V08D07
9	Visit 9 Follow-up Visit: Day 8 (72±2 hrs post-last dose)	8	Visit 9 (Day 8)	V09D08
10	Visit 10 Follow-up Visit: Day 12±2	10 ~ 14	Visit 10 (Day 12)	V10D12
11	Visit 11 Final Visit (Day 22±2, within 3 days after withdrawal)	22	Visit 11 (Day 22)	V11D22
-	Unscheduled Visit	-	-	V□□.□

(5) Full term for 'Protocol Deviation Code':

Code	Full Term
<to added="" be="" data="" final="" in="" real="" tabulation="" upon=""></to>	

(6) For clinical relevance

CS: abnormal and clinically significant LLN: lower limit of normal range NCS: abnormal but not clinically significant ULN: upper limit of normal range

(7) For Transition of Clinical Relevance

Relieved CS (Medical History or Adverse Event) at baseline to Normal / NCS at

visit.

Unchanged Including Normal at baseline to NCS at visit, NCS at baseline to Normal

at visit.

Worsened (Medical History) Normal / NCS at baseline to CS (Medical History) at visit

Worsened (Adverse Event) Normal / NCS / CS (Medical History) at baseline to CS (Adverse Event)

at visit

Version 1.0, 08-SEP-2022 Confidential
Protocol No.: Careseng 1370-01 Page 6 of 20 A2 Healthcare Taiwan Co.

Careseng 1370 for Healthy Volunteers

(8) Abbreviations of statistics

N: number of non-missing values Missing: number of missing values

Mean: mean of values

SD: standard deviation of values Q1: 25% quartile of values Q3: 75% quartile of values

Median: median of values

IQR: inter-quartile-range (IQR=Q3-Q1)

Min: minimum of values Max: maximum of values CI: confidence interval

Version 1.0, 08-SEP-2022 C Protocol No.: Careseng 1370-01 P

Careseng 1370 for Healthy Volunteers

14 TABLES AND FIGURES

- The texts in shaded Italic are for programming note.
- Column of Study Site includes {Site 1: TMUH}
- Column of Dose Level includes {A (1 sachet/day), B (2 sachets/day), C (3 sachets/day), D (1 sachet/day), Total} as appropriate
- Description in <...> will be presented according to data values.

14.1 DEMOGRAPHIC DATA AND BASELINE CHARACTERISTICS

14.1.1 Screen Failures and Subject Disposition by Study Site

Characteristics	Study Site
.All Screened Subjects	******
n	XXX
Eligible Subjects	XXX (XXX.X%)
Screening Failures	XXX (XXX.X%)
<screen 1="" failure="" reason=""></screen>	XXX (XXX.X%)
<screen 2="" failure="" reason=""></screen>	XXX (XXX.X%)
<screen 3="" failure="" reason=""></screen>	XXX (XXX.X%)
	XXX (XXX.X%)
.Population of Eligible Subjects	
n	XXX
ITT	XXX (XXX.X%)
MTD-Evaluable	XXX (XXX.X%)
Non-MTD-Evaluable	XXX (XXX.X%)
<reason 1=""></reason>	XXX (XXX.X%)
<reason 2=""></reason>	XXX (XXX.X%)
	XXX (XXX.X%)
Non-ITT	XXX (XXX.X%)
Daga Lavel of Elicikla Cukiasta	
.Dose Level of Eligible Subjects	XXX
A (1 sachet/day)	
	XXX (XXX.X%)
B (2 sachets/day)	XXX (XXX.X%)
C (3 sachets/day)	XXX (XXX.X%)
D (1 sachet/day)	XXX (XXX.X%)
. Protocol Deviation of Eligible Subjects	
n	XXX
Major Protocol Deviation	XXX (XXX.X%)
<protocol 1="" deviation=""></protocol>	XXX (XXX.X%)
<protocol 2="" deviation=""></protocol>	XXX (XXX.X%)
 Minor Protocal Deviation	VVV (VVV V0/)
Minor Protocol Deviation	XXX (XXX.X%)
<pre><pre><pre><pre><</pre></pre></pre></pre>	XXX (XXX.X%)
<protocol 2="" deviation=""></protocol>	XXX (XXX.X%)

ITT: Intent-to-Treat population, MTD-Evaluable: Maximum Tolerated Dose-Evaluable Population (subset of ITT)

Careseng 1370 for Healthy Volunteers

14.1.2 Study Visits, Study Termination, Subject Disposition and Protocol Deviation

Population: Intent-to-Treat Population	
Characteristics	Dose Level
. Study Termination	
n	XXX
Study Completed	XXX (XXX.X%)
Study Not Completed	XXX (XXX.X%)
Withdrew consent	XXX (XXX.X%)
Protocol issue	XXX (XXX.X%)
•••	XXX (XXX.X%)
. Study Duration [days]	
n (Missing)	XXX
Mean (SD)	XXX (XXX)
Median (IQR)	XXX (XXX)
Q1~Q3	XXX~XXX
Min~Max	XXX~XXX
.Population	*****
n NATE E 1 11	XXX
MTD-Evaluable	XXX (XXX.X%)
Non-MTD-Evaluable	XXX (XXX.X%)
<reason 1=""></reason>	XXX (XXX.X%)
<reason 2=""></reason>	XXX (XXX.X%)
	XXX (XXX.X%)
.Protocol Deviation	
n	XXX
Major Protocol Deviation	XXX (XXX.X%)
<protocol 1="" deviation=""></protocol>	XXX (XXX.X%)
<protocol 2="" deviation=""></protocol>	XXX (XXX.X%)
Minor Protocol Deviation	XXX (XXX.X%)
<protocol 1="" deviation=""></protocol>	XXX (XXX.X%)
<protocol 2="" deviation=""></protocol>	XXX (XXX.X%)
. Study Visits Completed, Adjusted Visits Completed	
N	XXX
Visit 1 (Screening)	XXX (XXX.X%)
Visit 2 (Day 1)	XXX (XXX.X%)
Visit 3 (Day 2)	XXX (XXX.X%)
Visit 4 (Day 3) Visit 5 (Day 4)	XXX (XXX.X%) XXX (XXX.X%)
Visit 5 (Day 4) Visit 6 (Day 5)	XXX (XXX.X%) $XXX (XXX.X%)$
Visit 7 (Day 6)	XXX (XXX.X%)
Visit 8 (Day 7)	XXX (XXX.X%)
Visit 9 (Day 8)	XXX (XXX.X%)
Visit 10 (Day 12)	XXX (XXX.X%)
Visit 11 (Day 22)	XXX (XXX.X%)

Study Duration [days] = Date of Termination - Visit 1, or alternatively as the last visit date - Visit 1 Adjusted Visits Completed: Visits except visit 8 and visit 9 not in its visit window are shifted to corresponding scheduled visits

Careseng 1370 for Healthy Volunteers

14.1.3 Demographic Data

Characteristics	Dose Level
. Study Sites	
n (Missing)	XXX (XXX)
Site 1: TMUH	XXX (XXX.X%)
. Variable, including Age [Y/O], Baseline Body Weight [kg]	, Height
[cm], BMI [kg/m^2]	
n (Missing)	XXX (XXX)
Mean (SD)	XXX (XXX)
Median (IQR)	XXX (XXX)
Q1~Q3	XXX~XXX
Min~Max	XXX~XXX
. Gender	
n (Missing)	XXX (XXX)
Male	XXX (XXX.X%)
Female	XXX (XXX.X%)
. Race (multiple selection)	
n (Missing)	XXX (XXX)
Black or African American	XXX (XXX.X%)
American Indian or Alaska Native	XXX (XXX.X%)
Asian	XXX (XXX.X%)
Native Hawaiian or Other Pacific Islander	XXX (XXX.X%)
White	XXX (XXX.X%)
Not Reported	XXX (XXX.X%)
Unknown	XXX (XXX.X%)

Age [Y/O] = int((date of informed consent - date of birth)/365.25)

BMI [kg/m 2]= Weight [kg] / (Height [cm]) $^2 * 10000$

Baseline is Visit 2 or alternatively as Visit 1 if Visit 2 data is not available

14.1.4 General Medical History, Concurrent Disease/Status and Chest X-Ray

Population: Intent-to-Treat Population

Characteristics	Dose Level
General Medical History	
n	XXX
At least one below	XXX (XXX.X%)
<body 1="" system=""></body>	XXX (XXX.X%)
<body 2="" system=""></body>	XXX (XXX.X%)
<body 3="" system=""></body>	XXX (XXX.X%)
<body 4="" system=""></body>	XXX (XXX.X%)
•••	
. Current Condition	
n	XXX
At least one below	XXX (XXX.X%)
<body 1="" system=""></body>	XXX (XXX.X%)
<body 2="" system=""></body>	XXX (XXX.X%)
<body 3="" system=""></body>	XXX (XXX.X%)
<body 4="" system=""></body>	XXX (XXX.X%)
•••	•••

Version 1.0, 08-SEP-2022 Protocol No.: Careseng 1370-01

Careseng 1370 for Healthy Volunteers

Characteristics	Dose Level
n (Missing)	XXX (XXX)
Normal	XXX (XX.X%)
NCS	XXX (XX.X%)
CS (Medical History)	XXX (XX.X%)
CS (Adverse Event)	XXX (XX.X%)
Not Interpretable	XXX (XX.X%)

Current condition lists the medical histories that are ongoing or with end date \geq date of visit 2

14.1.5 Prohibited Medications, Treatments, Procedures and Foods

For Prohibited Medications, categories are Surgery, Herbal Medications, Herbal Supplements, Herbal Medicinal Food, Other. For Prohibited Foods, refer to CRF for the categories.

Population: Intent-to-Treat Population

_ 1	
Characteristics	Dose Level
. Prohibited Medications, Treatments, Procedures	
. Prohibited Foods	
n (Missing)	XXX (XXX)
At least one below	XXX (XXX.X%)
<category 1=""></category>	XXX (XXX.X%)
<category 2=""></category>	XXX (XXX.X%)
<category 3=""></category>	XXX (XXX.X%)
<category 4=""></category>	XXX (XXX.X%)
	•••

14.1.6 Study Drug Administration, Compliance and Exposure

Population: Intent-to-Treat Population

Characteristics	Dose Level
.Total IP Administration [sachets],	
Treatment Duration [days]	
Treatment Compliance [%],	
Mean Daily Dose [sachet/day]	
n (Missing)	XXX
Mean (SD)	XXX (XXX)
Median (IQR)	XXX (XXX)
Q1~Q3	XXX~XXX
Min~Max	XXX~XXX
. Treatment Compliance	
n (Missing)	XXX (XXX)
<60%	XXX (XXX.X%)
60 ~ <80%	XXX (XXX.X%)
80 ~ <100%	XXX (XXX.X%)
100 ~ <120%	XXX (XXX.X%)
≥120%	XXX (XXX.X%)

- Treatment Duration [days] = the last dosing date the first dosing date + 1.
- Treatment Compliance [%] = Total IP Administration [sachets] / Dose Level [sachet/day] / Treatment Duration [days] * 100%
- Mean Daily Dose [sachet/day] = Total IP Administration [sachets] / Treatment Duration [days]

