#### 4. STUDY DESIGN

This study will be performed in healthy volunteers in a conventional 3+3 doseescalation design. There are total 4 cohorts in this study. Three cohorts (level A, B, and C) of up to 6 evaluable volunteers per cohort planned to be sequentially accrued to receive Careseng 1370 1, 2, and 3 sachets per day, 4,000 mg/sachet before meal (starting from 1 sachet, level A). One cohort (level D, modified cohort) of up to 6 evaluable volunteers per cohort will be planned to be accrued to receive 1 sachet of Careseng 1370 every other day (level D) when the dose de-escalates from level A. At least 5 days of staggering and with the investigator's judgement of no safety concern will be required to administer the next volunteer for the first three volunteers of each cohort. The staggering time starts from Day 1 of one volunteer to Day 1 of the next volunteer. Careseng 1370 should be taken around 1 hour before meal where the respective number of sachets and meals of each dose level are as follows:

- Level A (1 sachet): 1 sachet before breakfast
- Level B (2 sachets): 1 sachet before breakfast, 1 sachet before lunch
- Level C (3 sachets): 1 sachet before breakfast, 2 sachets before lunch
- Level D (1 sachet) (modified cohort): 1 sachet before breakfast on 1st, 3rd, and 5th days

Note:

1. Breakfast is defined as the first meal of the visit day while lunch is defined as the  $2^{nd}$  meal of the visit day in this study.

2. The modified cohort is the lower dose level below the starting dose level A. This cohort will be implemented when the dose de-escalates from level A.

The starting dose of Careseng 1370 (level A) is determined based on the results of the preclinical toxicity studies. Based on these data, the starting dose of Careseng 1370, 1 sachet containing 652 mg drug substance, is considered to be a safe starting dose in human. When the dose de-escalation was determined on level A, the modified cohort (level D) will be implemented. Volunteers will be followed from the start of Careseng 1370 administration up to Final visit (Day 22).

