# of sachets of study drug actually administered Total # of sachets of study drug assigned at that level × 100%

#### 6. STUDY MEASUREMENTS

#### 6.1 Eligibility

Eligibility should be thoroughly checked by the investigators at Screening visit and Day 1 visit.

If a volunteer is a screen failure, a minimal set of screen failure information is required to ensure transparent reporting of screen failure subjects, to meet the regulatory authority requirement and to respond to queries from regulatory authorities and IRBs/IECs. Minimal information includes demographics, screen failure details, concomitant medication, and any serious adverse event.

Re-screening for volunteer's eligibility will be allowed if the volunteer is willing to participate in the study and one of the following conditions meets:

- If a volunteer consents to participate and meets the eligibility criteria but a delay occurs in starting to participate in due to certain change in situation such that some measurement relevant to eligibility became invalid owing to the delay
- If the cause of screen failure has now resolved or adequately treated such that volunteer's conditions have now stabilized
- If there is an alternative manner to indicate that the volunteer may be suitable.

In these situations,

- A new eCRF will be used
- A new Screening number will be assigned to the person
- The person will be marked as having been re-screened on both the eCRF and the source document.
- The old eCRF will be completed as fully as possible following eCRF completion guide and data on the old eCRF is not copied to the new eCRF.
- The volunteer needs to sign a new ICF as part of the screening procedure.

It is not appropriate to re-screen a volunteer if he/she has previously failed to meet the eligibility criteria and no further changes or treatments have been able to indicate that the volunteer may be suitable.

Volunteer may be re-tested/measured for procedures relevant to causes of screen failure if investigator considers such causes can be resolved soon.

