1.2 Analysis Populations

According to the protocol, only Intent-to-treat (ITT) population was defined for analyses of primary and secondary endpoints.

Section 10.2.1 Analysis Population: Intent-to-treat (ITT) population:

- Volunteers receive any Careseng 1370

For maximal tolerated dose (MTD) determination, a MTD-Evaluable Population is defined as below according to protocol section 3.1 "Volunteers Enrollment" on DLT analysis.

MTD-Evaluable Population:

- 1. A subset of ITT population
- 2. Experiences DLT OR completes DLT observation period with at least 80% of study drug compliance and has exposed to Careseng 1370 for at least 4 days (level A, B, and C), OR completes DLT observation period with 100% of study drug compliance (level D).

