1.3 Treatment Compliance

Treatment compliance is defined as below in protocol section 5.6:

Volunteer's compliance will be assessed by the following formula:	
# of sachets of study drug actually administered	- × 100%
Total # of sachets of study drug assigned at that level	- × 100%

The parameters of compliance calculation are not well-defined in the protocol. The formula to derive treatment compliance and relevant parameters are adjusted as below:

```
Treatment Compliance = # of sachets of study drug actually administered

Dose Level [Sachet/Day] × Treatment Duration × 100%

[Days]
```

• Treatment Duration [Days] = the last dosing date - the first dosing date + 1.

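### The SAP's compliance formula scores a full Level D course at 60%, so, if Level D was opened, DLT-free completers drop out of the MTD-evaluable set while volunteers with a DLT stay in

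*SAP*

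**What the plan says.** Protocol 5.6 divides sachets taken by "Total # of sachets of study drug assigned at that level". Protocol section 4 has Level D volunteers "receive 1 sachet of Careseng 1370 every other day (level D"), on Days 1, 3 and 5, so three sachets are assigned.

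SAP 1.3 sets that formula aside, saying "The parameters of compliance calculation are not well-defined in the protocol". It divides instead by the daily dose level times the treatment duration, with "Treatment Duration [Days] = the last dosing date - the first dosing date + 1". SAP 14.1.6 repeats this: "Treatment Compliance [%] = Total IP Administration [sachets] / Dose Level [sachet/day] / Treatment Duration [days] * 100".

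The daily rate for Level D is given in the SAP instructions, item (2): "D (1 sachet/day): Careseng 1370 1 sachet before breakfast on 1st, 3rd and 5th days (modified cohort"). The same rate heads the table columns: "Column of Dose Level includes {A (1 sachet/day), B (2 sachets/day), C (3 sachets/day), D (1 sachet/day), Total} as appropriate". Table 14.1.1 and the listing instructions also carry it.

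The MTD-evaluable population is defined in two ways:

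- **SAP 1.2** follows Protocol 3.1. A volunteer qualifies by having a DLT. Without one, Levels A to C need completion of the DLT observation period, at least 80% compliance and at least 4 days of exposure. A Level D volunteer without a DLT qualifies if he or she "completes DLT observation period with 100% of study drug compliance (level D").
- **The table instructions, item (3), and the listing instructions, item (2),** keep the DLT route and otherwise ask only for 80% compliance and 4 days of exposure. They have no Level D clause and do not require the observation period to be completed.

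**The concern.** The SAP applies a once-daily rate to an every-other-day schedule. Two of the five days in the Level D denominator carry no planned dose, so full adherence cannot reach either compliance cut-off. A DLT bypasses the compliance test, so the formula in effect selects Level D volunteers by outcome: those with a DLT stay and those without one leave.

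Protocol 10.2.1 bases the MTD decision on DLTs in evaluable subjects. The SAP reports DLTs on that set (Tables 14.3.1.1 and 14.3.1.4), counts it with reasons for exclusion (Tables 14.1.1 and 14.1.2), and lists the excluded volunteers (Listing 16.2.3.2). These outputs would overstate the Level D DLT rate and contradict the ITT table beside them.

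There is a second weakness. The denominator runs only to the last dose actually taken, so it shrinks when a volunteer stops early. At Levels B and C this can lift a volunteer above 80% whom Protocol 4.3 would withdraw for being below it.

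**Working it through.** **Inputs.** Sachets assigned over Days 1 to 5 (Protocol 5.2): A 5, B 10, C 15, D 3. Daily rates in the SAP: A 1, B 2, C 3, D 1. Duration is last date minus first date plus 1.

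- Protocol compliance = sachets taken / sachets assigned.
- SAP compliance = sachets taken / (daily rate × duration).

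Neither document works an example, so there is no stated result to reproduce.

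**Full course at each level**

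| Level | Protocol | SAP |
|---|---|---|
| A | 5/5 = 100% | 5/(1 × 5) = 100% |
| B | 10/10 = 100% | 10/(2 × 5) = 100% |
| C | 15/15 = 100% | 15/(3 × 5) = 100% |
| D | 3/3 = 100% | 3/(1 × 5) = 60% |

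Only Level D disagrees. In Table 14.1.6 a complete Level D course falls in the 60 to below 80% band, with a mean daily dose of 3/5 = 0.6 under a column headed 1 sachet/day.

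**Level D, stopping early**

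| Last dose | Protocol | SAP |
|---|---|---|
| Day 1 | 1/3 = 33.3% | 1/(1 × 1) = 100% |
| Day 3 | 2/3 = 66.7% | 2/(1 × 3) = 66.7% |
| Day 5, all taken | 3/3 = 100% | 3/(1 × 5) = 60% |

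The SAP score falls as adherence rises.

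**Effect on the Level D DLT table.** Assume six volunteers, with all DLT-free ones fully compliant. Each DLT-free volunteer scores 60%, below both 80% and 100%, and is excluded.

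| DLTs | Protocol evaluable set | SAP evaluable set |
|---|---|---|
| 0 | 0 of 6 | nobody evaluable |
| 1 | 1 of 6 (17%) | 1 of 1 (100%) |
| 2 | 2 of 6 (33%) | 2 of 2 (100%) |

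**Exposure rule.** The short definition asks for at least 4 days. Level D has 3 dosing days over a 5-day span, so it fails if dosing days are counted and passes if the span is used. Correcting the formula alone therefore does not settle Level D under that wording.

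**Levels A to C.** With a last dose on Day 5 the two denominators are equal. A last dose before Day 4 fails the 4-day exposure rule. That leaves a last dose on Day 4, with dosing on each of Days 1 to 4. The two formulas then fall on different sides of 80% in three cases only:

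| Level, sachets taken | SAP | Protocol |
|---|---|---|
| B, 7 | 7/8 = 87.5% | 7/10 = 70% |
| C, 10 | 10/12 = 83.3% | 10/15 = 66.7% |
| C, 11 | 11/12 = 91.7% | 11/15 = 73.3% |

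Level A has none: 4/4 = 100% against 4/5 = 80%, and both pass. Adding one such DLT-free volunteer to a cohort with 1 DLT in 6 gives 1 of 7 (14%) instead of 1 of 6 (17%).

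**Would a different Level D rate repair the SAP formula?** A rate of 0.6 sachet/day gives 3/(0.6 × 5) = 100% for a full course, but 1/(0.6 × 1) = 167% after stopping on Day 1 and 2/(0.6 × 3) = 111% after stopping on Day 3. A rate of 0.5 gives 3/(0.5 × 5) = 120% for a full course. Neither works; a fixed denominator does.

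**The case against.** The 60% result is hard to dispute, so the case on the other side concerns consequence.

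- **Level D may never have opened.** It is used only on de-escalation from Level A, and the documents do not say whether that happened. This stands: without Level D, the main effect disappears.
- **No dosing decision depends on it.** The DSMB decides escalation under the protocol, and the SAP (08-SEP-2022) postdates the expected last exit (MAR2022). This stands.
- **The error would be visible.** The DLT tables print the ITT and evaluable sets whenever they differ, and exclusions are listed with reasons. This stands as mitigation, but two contradictory tables still need correcting.
- **Early stoppers at Level D do not become evaluable.** A DLT-free volunteer who stops after Day 1 scores 100%, but fails both the completion requirement in SAP 1.2 and the 4-day rule in the short definition. This stands: the reversed ranking distorts only the compliance rows of Table 14.1.6.
- **The Level B and C case fails under SAP 1.2.** A volunteer withdrawn for missing Day 5 should have the final visit within 3 days, about Day 8, and so does not complete the Day 1 to Day 10 window. This largely stands. Wrong inclusion needs the short definition, or a volunteer kept on study despite Protocol 4.3. However, the short definition is the one printed in the instructions for the tables and listings.
- **The link between formula and population is not explicit.** SAP 1.2 speaks of study drug compliance and SAP 1.3 of treatment compliance, with no cross-reference. But SAP 1.3 quotes the Protocol 5.6 formula and adjusts it, and it is the only compliance formula the SAP puts into force. The general statement that programming follows the latest protocol does not rescue the point, because SAP section 1 lists this as an exception to the protocol.

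**Conclusion.** The concern holds. Applied as written, the SAP scores a complete Level D course at 60% instead of 100%, and a DLT-free completer fails both versions of the MTD-evaluable rule. In a fully compliant cohort of six, the evaluable DLT rate becomes 100% with one or two DLTs, and the table is empty with none. This assumes that Level D enrolled volunteers and that the SAP 1.3 formula is the one used to build the evaluable set.

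If Level D was never opened, two lesser faults remain: the two MTD-evaluable definitions conflict, and the shrinking denominator can admit an under-dosed Level B or C volunteer under the short definition. The latter is uncommon. It needs a DLT-free volunteer who stops after Day 4 having already missed one or two sachets.

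The ITT DLT table and the DSMB's decisions are unaffected. This is a reporting error that should be corrected before the tables are final.

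**What to change.** 1. In SAP 1.3 and 14.1.6, define compliance as sachets taken divided by sachets assigned at that level: A 5, B 10, C 15, D 3. This is the Protocol 5.6 formula with its denominators written out. Full courses then score 100% at every level.
2. Relabel Level D as one sachet every other day (3 sachets over Days 1 to 5) in the dose-level instructions, the table column headings, Table 14.1.1 and the listing instructions.
3. Replace the short MTD-evaluable definition in the table and listing instructions with the SAP 1.2 text, including completion of the DLT observation period and the Level D clause.

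The cost is one formula, one label and one definition, with matching program changes and no new data. Volunteers who stop early for a DLT will show low compliance under the fixed denominator, but they remain evaluable because a DLT qualifies on its own.
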